3 OBJECTIVES AND ENDPOINTS

OBJECTIVES	ENDPOINTS	JUSTIFICATION FOR ENDPOINTS
Primary		

 To assess the efficacy of Galnobax® in terms of proportion of Subjects achieving Target Ulcer Closure within 12-week Treatment Phase upon application of Galnobax® plus Standard of Care as against only Standard of Care treatment, as assessed by the blinded Investigator 	
The efficacy assessment will involve Galnobax® plus Standard of Care and only Standard of Care groups
 
Efficacy endpoints:
 
Proportion of subjects achieving Target Ulcer Closure within 12-week Treatment Phase, as assessed by blinded Investigator
	Complete wound closure of a chronic, nonhealing wound is one of the most important objective and clinically meaningful wound healing endpoint
Secondary		
Efficacy	Efficacy endpoints	

 To compare Time to Target Ulcer Closure within the 12-week Treatment Phase, upon application of Galnobax® plus Standard of Care as against only Standard of Care treatment, as assessed by the blinded Investigator 	
 Time to Target Ulcer Closure during the 12-week Treatment Phase, as assessed by the blinded Investigator 	This endpoint evaluates clinically meaningful reduction in the time to Target Ulcer Closure using a time-to-event analysis (the event being first observation of complete closure)

 To compare proportion of Subjects achieving Target Ulcer Closure till End of Study upon application of Galnobax® plus Standard of Care as against only Standard of Care treatment, as assessed by the blinded Investigator 	
 Proportion of Subjects achieving Target Ulcer Closure till End of Study, as assessed by the blinded Investigator 	This endpoint is for evaluating sustained effect of the treatment post its discontinuation
Safety		

 To investigate the safety of Galnobax® treatment during the Study 	
 Proportion of Subjects with treatment emergent adverse events (TEAEs) 	This endpoint evaluates safety of Galnobax® by assessing TEAEs

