8.2.4 TIME PERIOD AND FREQUENCY FOR EVENT ASSESSMENT AND FOLLOW-UP

The occurrence of an adverse event (AE) or serious adverse event (SAE) may come to the attention of Study personnel during Study visits or Study Nurse during visits to Subject and interviews of a Study Subject presenting for medical care, or upon review by a study monitor.

All AEs including local and systemic reactions not meeting the criteria for SAEs will be captured on the appropriate electronic case report form (eCRF). Information to be collected includes duration (start and end dates), severity/intensity, relationship to IP, specific therapy, results and consequences and seriousness. All AEs occurring while on Study must be documented appropriately regardless of relationship. All AEs will be followed to adequate resolution.

Any medical condition that is present at the time that the participant is screened or before application of first dose will be considered as baseline and not reported as an AE. However, if the Study participant's condition deteriorates at any time during the study, it will be recorded as an AE.

Changes in the severity of an AE will be documented to allow an assessment of the duration of the event at each level of severity to be performed. AEs characterized as intermittent require documentation of onset and duration of each episode.

The Investigator will record all reportable events with start dates occurring any time after informed consent is obtained till the last day of Study participation. At each Study visit, the Investigator will inquire about the occurrence of AE/SAEs since the last visit. Events will be followed for outcome information until resolution or stabilization. An AE can reach one of the following outcomes:

- a. Complete recovery (AE/ SAE end date will be captured).
- b. Recovered with sequelae. (AE/ SAE end date will be captured and the sequelae will be specified).
- c. Ongoing
- d. Death
- e. Unknown: The outcome of the event may be captured as unknown only in the exceptional cases when the Subject is lost to follow-up (AE end date will be left blank).

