9.4.4 SAFETY ANALYSES

Safety will be analyzed for all Subjects in ITT Population in the three groups. No formal statistical analysis will be performed.

To investigate the safety of Galnobax® vehicle for establishing non-deleterious effects of Vehicle on wound healing, number and percentage of events as well as number and percentage of Subjects with events related to local wound assessment (local pain, edema, erythema) of Target Ulcer in Vehicle plus SoC group will be tabulated and reported.

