9.4.4.1 TREATMENT EMERGENT ADVERSE EVENT

Treatment emergent adverse events (TEAE) are undesirable events not present prior to medical treatment, or an already present event that worsens either in intensity or frequency following the treatment. The TEAEs, which is defined as all AEs on or after the application of first dose of IP will be summarized according to the numbers and percentages of TEAEs as well as numbers and percentages of Subjects with one or more occurrences of TEAEs during the Study. Number of Subjects with TEAEs and number of events of TEAEs will be tabulated by preferred term (PT) and system organ class (SOCL). If a Subject had more than one TEAE, event will be counted only once in SOCL and once for each PT.

Summaries of TEAEs by severity grade, relationship to Study medication, leading to death, SAEs of study, IP related TEAEs will be provided.

Also, summarization for SAE, SAEs by severity, SAEs by relationship to Study IP will be provided separately.

Listing will be provided for all Subjects who have at least one adverse event.

AEs will be coded using the MedDRA, version 20.0 or later.

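### Section 9.4.4.1 promises event counts of TEAEs, but its counting rule, read literally, turns them into subject counts

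*Combined protocol and SAP*

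**What the plan says.** Section 9.4.4.1 first promises an overall summary: "numbers and percentages of TEAEs as well as numbers and percentages of Subjects with one or more occurrences of TEAEs during the Study". It then describes the table by coded term: "Number of Subjects with TEAEs and number of events of TEAEs will be tabulated by preferred term (PT) and system organ class (SOCL". So two counts are intended in each row, one of subjects and one of events.

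The next sentence gives the only counting rule in the section: "If a Subject had more than one TEAE, event will be counted only once in SOCL and once for each PT". It does not confine itself to the subject column, and no other section gives a rule for the event column.

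Three other statements bear on the point:

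- Section 8.2.4, on recording: "AEs characterized as intermittent require documentation of onset and duration of each episode".
- Section 3, on the safety endpoint, which is a subject-level measure: "Proportion of Subjects with treatment emergent adverse events (TEAEs".
- Section 9.4.4, on inference for safety: "No formal statistical analysis will be performed".

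**The concern.** If the event is counted once per PT for each subject, the event count for that PT is the number of affected subjects. The second promised column then adds nothing to the first. In the SOC row, a subject contributes one event however many terms or episodes fall in that class.

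Recurrence is what an event count is meant to show. Treatment is applied twice daily for up to 12 weeks, and infection of a target or non-target ulcer is to be reported as an AE (section 8.2.3.3). Section 8.2.5 also makes out-of-range changes in laboratory values, vital signs and ECG reportable whatever the Investigator thinks of their clinical significance, so repeat events in one subject are plausible. Section 8.2.4 has the episodes recorded, but the rule as worded would drop the repeats from the SOC and PT tables. At stake is the accuracy of a descriptive table. No test, endpoint or sample-size result depends on it.

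**Working it through.** The plan states no TEAE count or rate for this trial, so there is no figure to reproduce. The check compares a full event count with the count under the literal rule.

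**1. One subject.** Suppose a subject has three PTs in one SOC, with two episodes of each.

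- Full count: 3 × 2 = 6 events.
- Literal rule, summed over PT rows: 3.
- Literal rule, SOC row: 1.

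**2. One PT row.** Let k be the number of affected subjects and m the mean episodes per affected subject. The full count is k·m and the literal rule gives k. The fraction lost is (k·m − k)/(k·m) = (m − 1)/m.

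| m | 1 | 1.5 | 2 | 3 | 4 |
|---|---|---|---|---|---|
| Lost | 0% | 33% | 50% | 67% | 75% |

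The values of m are illustrative; the documents give none.

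**3. Between-arm comparison in one PT row** (assumed inputs).

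| Case | Arm A | Arm B | Full events A vs B | Literal rule A vs B |
|---|---|---|---|---|
| a | 30 subjects × 2 | 30 × 1 | 60 vs 30, ratio 2.0 | 30 vs 30, ratio 1.0 |
| b | 36 × 2 | 30 × 2 | 72 vs 60, ratio 1.2 | 36 vs 30, ratio 1.2 |
| c | 20 × 3 | 60 × 1 | 60 vs 60, ratio 1.0 | 20 vs 60, ratio 0.33 |

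In case (a) the arms look closer than they are. In case (b) the ratio is unchanged and the difference falls from 12 to 6. In case (c) the arms look further apart. The direction is therefore not fixed.

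**4. SOC rows.** The only AE rate in the documents is in section 2.3.1: 29 AEs in 44 Phase 1/2 subjects, so M = 29/44 = 0.66 per subject. Two things have to be assumed:

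- Events per subject are Poisson, with a gamma-distributed mean (shape 1).
- Events fall into eight SOCs with weights w = 0.35, 0.20, 0.15, 0.10, 0.08, 0.06, 0.04 and 0.02.

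The chance that a subject has at least one event in a SOC is then Mw/(1 + Mw), and the expected SOC-level count under the rule is the sum of this over the SOCs.

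- At M = 0.66: 0.187 + 0.116 + 0.090 + 0.062 + 0.050 + 0.038 + 0.026 + 0.013 = 0.58. As a share of all events this is 0.5825/0.6591 = 88.4%, so about 12% are lost.
- At M = 1, 2 and 4, the same sum gives 0.836, 1.453 and 2.336, which is 83.6%, 72.6% and 58.4% of all events. The losses are 16%, 27% and 42%.
- If one arm has twice the Phase 1/2 rate (1.32 vs 0.66), the tabulated ratio is 1.050/0.583 = 1.80 in place of 2.0.

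**The case against.** The strongest reply is that the sentence is a misworded rule for counting subjects. It opens with the case of a subject who has more than one TEAE, and the sentence before it promises a separate event count that the literal reading would empty of content. This stands as a possibility, so a reader should not infer that an undercount is settled. But if that is what was meant, the plan has no stated rule for the event column, and the same rewording is needed. Section 9.4.1 defers detailed methods to a separate SAP, which is not among the documents reviewed and may resolve the matter.

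Four stronger readings are tempting, and the documents do not support them.

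- **That the rule makes the arms look alike.** Case (c) shows the opposite can happen.
- **That the rule governs the severity and relationship summaries, so that a severe episode is the one dropped.** Those summaries are promised in a separate paragraph that carries no counting rule. What can be said is that no worst-grade convention is stated.
- **That these tables are the whole safety result.** Section 9.4.4.1 also plans SAE summaries and a listing: "Listing will be provided for all Subjects who have at least one adverse event". Sections 9.4.4.2 and 9.4.4.3 add laboratory and vital-sign tables. Section 9.4.4 tabulates both events and subjects for local pain, edema and erythema in the Vehicle group, without a once-only rule.
- **That losses of 16% to 42% are to be expected.** Those figures need 1 to 4 events per subject, against 0.66 in Phase 1/2. The wider reporting rule in section 8.2.5 could raise the rate, but by how much is unknown.

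**Conclusion.** The point holds as a minor matter of reporting accuracy. Section 9.4.4.1 promises event counts and then gives a rule that, followed as written, replaces them with subject counts in each PT row and with fewer still in each SOC row. The loss per PT is (m − 1)/m and is zero only if no subject has a repeat. The SOC-level figure of about 12% rests on the Phase 1/2 rate carrying over and on an assumed event distribution and assumed SOC weights, so it is an illustration of size and not a forecast.

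The rule is stated per SOC and PT, and the text does not clearly extend it to the overall number of TEAEs. The proportion of subjects with TEAEs does not change under either reading, and with episodes recorded and listed, a correct event count could be recovered.

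**What to change.** Replace the counting sentence in section 9.4.4.1 with two statements. For counts of subjects, a subject is counted once per SOC and once per PT. For counts of events, every TEAE episode is counted, including repeats in the same subject. Carry the same wording into the separate SAP.

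As an optional clarification, state that subject-level summaries by severity and relationship use the worst grade and the closest relationship within each SOC and PT.

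The cost is one or two sentences before database lock. No new data are needed, because section 8.2.4 already has the episodes recorded, and no endpoint, test or sample size changes. Reported event totals would be larger than under the literal rule wherever subjects have repeat events.

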9.4.4.2 CLINICAL LABORATORY TEST

The clinical laboratory tests will be summarized descriptively for each of the continuous parameter at Subject's visits when tests are carried out for the changes from the baseline parameter. Shift tables in terms of counts and percentages will be presented at each relevant visit versus baseline for categorical laboratory parameters.

Individual data listings of laboratory results will be presented for each Subject. Clinically significant laboratory test abnormalities that are considered AEs by the Investigator will be presented in the AE listings.

9.4.4.3 PHYSICAL EXAMINATION AND VITAL SIGNS

The vital sign parameters will be summarized descriptively for each of the continuous parameters at each visit and for change from baseline.

The frequency counts and percentages of Normal, Abnormal NCS, and Abnormal CS will be provided for each body system of the physical examination.

Subject wise data listing will be provided for all vital sign parameters and physical examination.

9.4.5 BASELINE DESCRIPTIVE STATISTICS

The demographic and baseline characteristics will be summarized and listed for all Subjects in ITT Population.

Medical history will be coded using Medical Dictionary for Regulatory Activities (MedDRA) dictionary version 20.0. The count and percentage of Subjects will be summarized according to the coded terms of system organ class and preferred term across all the treatment groups.

The prior and concomitant medications will be coded using World Health Organization Drug Dictionary (WHODD)-September, 2016 or later. The count and percentage of Subjects will be summarized according to the coded terms of system organ class and preferred term across all the treatment groups.

Other baseline parameters like ECG and X-Ray will be listed as appropriate.

9.4.6 PLANNED INTERIM ANALYSES

No interim analysis is planned for this Study.

9.4.7 METHODS USED FOR MISSING DATA

Missing data points will be dealt with using appropriate statistical techniques, depending on the nature of the data and will elaborately explained in statistical analysis plan (SAP).

9.4.8 HANDLING OF OUTLIER DATA

The outlier data will be dealt with using appropriate statistical techniques, depending upon the nature and type of data and will elaborately explained in statistical analysis plan (SAP).

9.4.9 HANDLING OF TREATMENT FAILURE

Subjects with need for more than two surgical debridement procedures during Treatment Phase will be considered as treatment failure for the Subject.

9.4.10 STATISTICAL ANALYSIS OF DATA

The CRO will perform the statistical evaluation using appropriate statistical tests. Statistical analysis will be performed using SAS® system Version 9.4 software (SAS Institute Inc., NC, and USA) or later.

9.4.11 SUB-GROUP ANALYSES

The subgroup analysis for ulcer type (plantar and non-plantar) and ulcer size ($<5 \text{ cm}^2$ vs. $\geq 5 \text{ cm}^2$) will also be performed for the primary efficacy endpoint i.e. proportion of Subject achieving Target Ulcer Closure within 12-week Treatment Phase by considering ulcer type (plantar and non-plantar) and ulcer size ($<5 \text{ cm}^2$ vs. $\geq 5 \text{ cm}^2$) as the subgroup strata.

9.4.12 TABULATION OF INDIVIDUAL PARTICIPANT DATA

Listing of individual Subject data per visit (wherever applicable) for all key variable will be presented.

9.4.13 EXPLORATORY ANALYSES

Not applicable

10 SUPPORTING DOCUMENTATION AND OPERATIONAL CONSIDERATIONS

10.1 REGULATORY, ETHICAL, AND STUDY OVERSIGHT CONSIDERATIONS

10.1.1 INFORMED CONSENT PROCESS

The method of explanation to the Subject/legally accepted representative (LAR)/impartial witness and obtaining their consent would comply with the ICH GCP Guidelines, with GCP for Clinical Research in India, 2001; Indian Council of Medical Research's (ICMR) Ethical Guidelines for Biomedical Research on Human Participants, 2006 and Schedule Y, Amended 2005 under Drugs and Cosmetics Act and Rules there under, and the ethical principles in the amended Declaration of Helsinki version 2013.

10.1.1.1 CONSENT/ASSENT AND OTHER INFORMATIONAL DOCUMENTS PROVIDED TO PARTICIPANTS

Consent forms describing in detail the Study intervention, Study procedures, and risks are given to the potential participant and written documentation of informed consent is required from the Subject/LAR prior to starting intervention/administering Study intervention.

10.1.1.2 CONSENT PROCEDURES AND DOCUMENTATION

Prior to any Study-related Screening procedures being performed on the Subject, written informed consent will be obtained from each Subject before enrolling in the Study. The site should first obtain consent from the Subject/LAR on video recording of consent process. The Investigator or his/her representative will explain the nature of the Study to the Subject and the LAR (including the impartial witness if required) and answer all questions regarding this Study. This consent process will be video recorded by the site and stored carefully for any regulatory audit. The information and consent form will be reviewed, signed and dated by the Subject/LAR. In case the Subject or the LAR is illiterate, the impartial witness will attend the informed consent process and sign and date the ICF.

10.1.1.3 ETHICAL CONSIDERATION

The Study will be conducted according to the approved protocol (and amendments, if applicable), GCP standards (Good Clinical Practice Guidelines for Clinical Trials in India, FDA Title 21 part 312 and International Conference on Harmonization guidelines) and all applicable Government regulations.

The protocol will be submitted for review to EC of each site and their suggestions on Subject safety will be reviewed and adopted. Upon approval of protocol by EC, site will be initiated and Subjects will be randomized.

10.1.2 STUDY DISCONTINUATION AND CLOSURE

The Sponsor reserves right to terminate the Study at any time. The Principal Investigator (PI) and the Sponsor, if appropriate can mutually decide premature termination of the Study. The regulatory authorities or ECs may also recommend the Study termination before completion.

In the event of an early termination of the Study,

1. Investigators will cease the use of the IP immediately.

2. All outstanding electronic case report forms (eCRFs) will be completed and returned to the CRO/the Sponsor together with completed IP inventory, records and remaining Study material.
3. The CRO/the Sponsor will inform regulatory authorities reasons for such termination
4. Investigators will inform to respective ECs
5. The reason for termination will also be communicated to the Subjects in the trial.

Stopping or Discontinuation Rules for a Study Site:

The Study may be halted at any Study site if,

1. A Study site and/or its participating personnel are non-compliant with respect to
 - following the defined clinical Study protocol
 - reporting any adverse or unforeseen event to the EC/Regulatory in the minimum mandatory time or reporting AEs/Subject non-compliance to the CRO/the Sponsor
 - non-cooperation of the Investigator and/or Site with the CRO/the Sponsor
 - timely providing SoC to the Subjects
 - negligence to Subject's health and protocol by the Investigator/unblinded Investigator/site personnel involved in the Study
2. There is a significant decrease in the number of compliant Subjects anytime during the ongoing Study
3. If the Study Site / members of the site compromise(s) on the dignity or integrity of a Subject recruited into the Study
4. The EC recommends stop of Study based on occurrence of serious and unforeseen AEs

Stopping or Discontinuation Rules for a Full Study:

The Sponsor reserves right to discontinue the Study at any time.

10.1.3 CONFIDENTIALITY AND PRIVACY

The CRO and the Sponsor will affirm and uphold the principle of the Subject's right to protection against the invasion of privacy. Throughout this Study and any subsequent data analyses, all data reported to the Sponsor will be identified only by protocol number, Subject number and Subject initials.

The records of the Subject's medical history, physical examination, laboratory results and any other information or data generated during the Study will be made available to the Sponsor or its designee (auditors, monitors), the EC. It will also be made available to drug regulatory bodies in India and possibly other countries, formulary committees of hospitals, at the opinion of the Sponsor. A pre-condition for entry into this Study will be Subject's agreement to release the documentation and data for any lawful purpose. In such cases, the Subject's name will be removed from all documentation to ensure anonymity.

10.1.5 CLINICAL MONITORING

10.1.5.1 SITE INITIATION

Upon obtaining EC approval for a site, a “Site Initiation Visit” will be held before the first Subject is enrolled. The Subjects cannot be recruited at the site until occurrence of such visit and its documentation. During this visit, requirements of GCP, protocol procedures, and all logistic issues will be discussed at length. The availability of IP and supplies at the site will be ensured and documented. The training of Investigator, site staff and Study Nurse will be documented.

The CRO team will also determine the adequacy and readiness of the clinical Study facility to start enrolment. The team will discuss the responsibilities of the blinded and unblinded Investigators and Study Nurse as well as other personnel involved with the Study with regard to protocol adherence.

10.1.5.2 STUDY MONITORING AND SOURCE DATA VERIFICATION

After the Study is initiated, Study monitor(s) from the CRO will contact the Investigator to obtain information on the performance of the Study. These contacts will be scheduled at regular intervals and be either in person or telephonic.

Subsequent to start of recruitment, the first “Monitoring Visit” would occur as soon as possible after recruitment of the first Subject. The monitoring visits will take place at regular intervals during the entire Study (once a month or once in two months depending on recruitment rate of the site).

The Investigator and site staff are obliged to set aside adequate time and place for the monitoring visits. All Study related site records where original entries are made will be reviewed to make sure that all Study related compliances are met.

In addition to the monitoring visits, the sites may be audited or inspected. The audit may be carried out by the Quality Assurance Department of the CRO and/or independent entity authorized by the Sponsor. In addition, regulatory authorities may inspect the Study. The Investigator undertakes to expeditiously inform the CRO of an inspection by a regulatory authority.

